#### ***Length of Hospital Stay***

Hospital length of stay will be defined as time from study enrollment to first hospital discharge. We will follow the same analytical plan for the length of ICU stay outcome.

### ***Length of Oxygen Therapy in Hours***

### ***Length of Non-invasive Mechanical Ventilation***

We will provide median and range of length of non-invasive mechanical ventilation separately for each treatment group. There is an expectation that some patients will not require mechanical ventilation; therefore, overall duration of mechanical ventilation will be modeled with a zero-inflated Poisson model using consent and post-infusion start time for two separate analysis.

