Exclusion Criteria:	
 1. Subject unable to provide consent. 2. Patient, surrogate, or physician not committed to full support. 3. Malignant or other irreversible condition and estimated 28-day mortality $\geq 50\%$ 4. Moribund patient not expected to survive 48 hours (as defined by the primary medical team) from the start of study infusion 5. End-stage Liver Disease as defined by Child-Pugh Score > 9 6. Currently enrolled in, or having participated, in another study of an investigational compound within the last 30 days 7. Pregnant female or female who is breastfeeding 8. Allergy to L-citrulline or arginine or any citrulline- or arginine-containing product 9. Patient not otherwise suitable for the study in the opinion of any of the investigators 10. Requirement for intubation and invasive mechanical ventilation prior to study enrollment

Primary Clinical Efficacy Variables:	
The primary clinical efficacy variable is time to intubation event in hours from the start of study infusion.
 
Primary efficacy variables will be evaluated comparing intravenous L-citrulline vs. placebo in separate analyses.

Primary Biochemical Efficacy Variables:	
The primary biochemical efficacy variable is plasma levels of citrulline that are associated with primary and secondary clinical efficacy outcomes. It may serve as a surrogate marker for response.

Primary Safety Variable:	
Primary safety variable is hemodynamic status, specifically worst vasopressor dependency index through day 10.

Secondary Clinical Efficacy Variables:	
 1. All-cause hospital mortality 2. The requirement for intubation and invasive mechanical ventilation 3. Length of non-invasive mechanical ventilation in hours 4. Length of oxygen therapy in hours 5. Length of ICU stay in hours 6. Length of hospital stay in hours 7. Difference in proportion of patients intubated 8. Difference in proportion of patients intubated and on MV 9. Duration of mechanical ventilation from consent & post-infusion
Secondary Biochemical Efficacy Variables:	
 1. Plasma levels of citrulline and arginine at 2 hours, 12 hours, and study days 2, 4, 6, 8, 10. 2. Plasma NOx levels at 2 hours, 12 hours, and study days 2, 4, 6, 8, 10. 3. PK-PD analysis/modeling will enable dose proportionality (dose-response effect) determinations for a follow on confirmatory trial.

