10.6.1 Secondary Clinical Endpoints

All-cause, hospital mortality, defined by whether the patient was discharged from the hospital alive or deceased, will be analyzed via two statistical methods. The proportion of patients who have died by hospital discharge will be analyzed using a Chi-square analysis or Fisher's Exact Test, if needed. In addition, time to death will also be analyzed using a log-rank method of a Kaplan-Meier analysis. ICU length of stay (LOS) will be defined in days as the time from study enrollment to the day ICU discharge orders are written, regardless of when the patient physically leaves the ICU. Comparison will be made between the two groups for total ICU length of stay which will include any days of ICU re-admission prior to hospital discharge. Hospital length of stay will be defined as time from study enrollment to first hospital discharge. We will consider both ICU LOS and hospital LOS as count measure and has the potential to follow a skewed distribution. Initially, we will assess the distributional assumption. We will use a generalized linear model (GLM) to compare the expected ICU LOS and hospital LOS between the two treatment groups (placebo and intravenous citrulline). Specifically, we will use a negative binomial distribution and log-link to account for potential over-dispersion. We will report point estimates for the group mean difference along with a 95% confidence interval. Overall duration of mechanical ventilation will be modeled with zero-inflated Poisson or negative binomial method using consent and post-infusion start time for two separate analysis.

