## STUDY ENDPOINTS AND COVARIATES

**Table 1: Primary and Secondary Efficacy Endpoints**

Primary Clinical Efficacy Variables:	The primary clinical efficacy variable is time to intubation event in hours from the start of study infusion.
Secondary Clinical Efficacy Variables:	

1. All-cause hospital mortality

2. The requirement for intubation and invasive mechanical ventilation

3. Length of non-invasive mechanical ventilation in hours

4. Length of oxygen therapy in hours

5. Length of ICU stay in hours

6. Length of hospital stay in hours

7. Difference in proportion of patients intubated

8. Difference in proportion of patients intubated and on MV

Secondary Biochemical Efficacy Variables:	

1. Plasma levels of citrulline at 2 hours, 12 hours, and study days 2, 4, 8, 10.

2. Plasma levels of arginine at 2 hours, 12 hours, and study days 2, 4, 8, 10.

3. Plasma NOx levels at 2 hours, 12 hours, and study days 2, 4, 8, 10.

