## **SECONDARY ENDPOINTS**

### **Secondary Clinical Endpoints**

- All-cause hospital mortality
- The requirement for intubation and invasive mechanical ventilation
- Difference in proportion of patients intubated
- Difference in proportion of patients intubated an on MV
- Length of ICU stay in hours
- Length of hospital stay in hours
- Length of oxygen therapy in hours
- Length of non-invasive mechanical ventilation in hours

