#### ***Length of ICU Stay***

ICU length of stay (LOS) will be defined in days as the time from study enrollment to the day ICU discharge orders are written, regardless of when the patient physically leaves the ICU. Comparison will be made between the two groups for total ICU length of stay which will include any days of ICU re-admission prior to hospital discharge. We will consider ICU LOS a count measure and has the potential to follow a skewed distribution. Initially, we will assess the distributional assumption. We will use a generalized linear model (GLM) to compare the expected ICU LOS between the two treatment groups (placebo and intravenous citrulline). Specifically, we will use a negative binomial distribution and log-link to account for potential over-dispersion. We will report point estimates for the group mean difference along with a 95% confidence interval.

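### The SAP models overall ventilation duration with a zero-inflated Poisson only, naming no unit and making no allowance for over-dispersion, so its standard errors and p-values depend on an unstated choice

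*SAP*

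**What the plan says.** In the SAP, under Length of Non-invasive Mechanical Ventilation, "overall duration of mechanical ventilation will be modeled with a zero-inflated Poisson model". The model is run twice, once from consent and once from the start of infusion. The reason given is that some patients will need no ventilation. No unit, dispersion check, alternative distribution, robust standard error or tested parameter is named.

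Protocol section 10.6.1 left the choice wider for the same variable: "modeled with zero-inflated Poisson or negative binomial method". Protocol section 2.0 lists it without a unit, as "Duration of mechanical ventilation from consent & post-infusion".

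The neighbouring SAP endpoints are handled differently. For ICU stay, "we will use a negative binomial distribution and log-link to account for potential over-dispersion". For hospital stay, "We will follow the same analytical plan for the length of ICU stay outcome".

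The units around this variable are mixed:
- The heading under which the model sits is an endpoint listed in hours: "Length of non-invasive mechanical ventilation in hours".
- ICU stay is listed in hours, as "Length of ICU stay in hours", but for its count model "ICU length of stay (LOS) will be defined in days".

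**The concern.** A Poisson count part sets the variance equal to the mean. Zero inflation relaxes this only for patients with no ventilation at all. Among ventilated patients the constraint remains. For a duration it cannot hold in every unit: converting days to hours multiplies the mean by 24 and the variance by 576, so the variance-to-mean ratio rises 24-fold for the same patients. The Poisson standard error ignores this, and the p-value and interval therefore depend on how time is recorded.

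The SAP's authors saw over-dispersion as a risk for ICU and hospital stay in these same patients, but made no provision for it here. At stake is the validity of the p-value and confidence interval for one secondary variable, in both of its analyses.

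**Working it through.** The documents state no operating characteristic for this analysis beyond the general two-sided 0.05 level (SAP, Statistical Significance), so there is no planned figure to reproduce.

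**Inputs**
- Spread among ventilated patients: median 10 days, IQR 7 to 12 (Protocol section 3.4 on COVID-19 respiratory failure). This is the only spread for ventilation duration in the documents. It comes from 18 invasively ventilated patients in an ICU series.
- 60 patients, 1:1 (SAP, Sample Size).
- Assumed: no true effect; treatment tested in the count part; model-based standard errors.

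**Formulae**
- SD ≈ IQR/1.349 = (12 − 7)/1.349 = 3.71 days.
- Dispersion φ = SD²/mean. Changing from days to hours multiplies φ by 24.
- True size of a nominal 5% test = 2 × [1 − Φ(1.96/√φ)].

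**Results at mean 10 days**

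| SD (days) | φ, days | size, days | φ, hours | size, hours |
|---|---|---|---|---|
| 3 | 0.90 | 3.9% | 21.6 | 67% |
| 3.71 | 1.37 | 9.4% | 33.0 | 73% |
| 5 | 2.50 | 22% | 60.0 | 80% |
| 7 | 4.90 | 38% | 117.6 | 86% |

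Taking the mean as (7 + 10 + 12)/3 = 9.67 days instead moves the second row to 10.0% and 73.7%. At that row the reported standard error is too small by a factor √φ of about 1.2 in days and 5.7 in hours.

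**Check by simulation.** Durations came from a gamma fitted to the quoted quartiles or from a normal distribution, with 30 per arm and 50% to 86% ventilated. The test of the count part rejected in 9.6% to 10.2% of null data sets in days and 73.0% to 75.1% in hours. With true Poisson data it rejected in 4.7% to 5.1%, so the excess comes from the unmodelled dispersion. A joint test of the count and zero parts gave 8.3% to 9.5% in days and 70.2% to 72.4% in hours, so which part is tested matters less than the unit.

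**Effect of Hochberg, as an illustration.** Take a nine-member family: the eight secondary clinical variables in SAP Table 1 plus this one. At the strictest step the level is 0.05/9 = 0.0056, with z = 2.77. The rejection rate is 2 × [1 − Φ(2.77/√1.37)] ≈ 2% in days and 2 × [1 − Φ(2.77/√33.0)] ≈ 63% in hours.

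**Interval width, 75% ventilated (22.5 per arm).** The Poisson SE of the log ratio in days is √(2/(22.5 × 10)) = 0.094, a 95% factor of exp(1.96 × 0.094) = 1.20. Scaled by √1.37 it is 0.1105, a factor of 1.24. In hours the Poisson factor is 1.04; scaled by √33.0 the SE is again 0.1105 and the factor 1.24. Scaling removes the dependence on the unit.

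**The case against.** The strongest reply is that no passage assigns hours to overall duration. The hours label belongs to the length of non-invasive ventilation, for which the SAP promises a median and range. The closest precedent, the ICU-stay count model, uses days. In days the excess is modest and may be absent. This stands: the 73% figure describes what follows if hours were chosen, not what the plan says. The choice is nevertheless open, because the model sits under an endpoint listed in hours.

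Second, the spread is borrowed. It may not fit patients admitted to the floor without intubation (Protocol section 6.2), or a duration that counts high-flow and BiPAP support (SAP secondary objectives). This also stands, and is why the days figure is given as a range.

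Third, Hochberg applies to secondary outcomes. It lowers the chance of a false claim in days. It needs valid p-values to work on, however, and leaves the confidence interval unchanged. Overall duration also appears in neither SAP Table 1 nor the list under Secondary Clinical Endpoints, so its place in the Hochberg family is unclear.

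Fourth, zero-inflated Poisson is one of the options in Protocol section 10.6.1. A reader might infer that the SAP contradicts the protocol. It does not; it narrows the choice to the option without a dispersion parameter.

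**Conclusion.** The point holds as a defect in the specification of one secondary analysis. As written, the rule can give invalid standard errors, and how invalid depends on a unit left to the analyst. Under the borrowed ICU spread, with a count-part test and model-based standard errors, the unadjusted false-positive rate is about 10% in days (about 4% at SD 3 to 22% at SD 5) and about 73% in hours (67% to 86% for SD 3 to 7). These rates are per test. The consent and infusion-start analyses use largely the same data and should not be counted as independent chances of error.

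Two stronger readings are not supported. A reader might take 10% or 73% as the trial's actual error rate, but the documents fix neither the unit, the spread in this population nor the tested parameter. A reader might also treat this as a primary-endpoint problem, because one clause in Protocol section 10.5 offers ventilation duration as an alternative primary. Protocol sections 2.0 and 4.1 and the SAP's primary endpoint sections name only time to intubation, and the point does not rest on that clause.

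**What to change.** In the SAP paragraph on ventilation duration:
1. State the analysis unit. Days would match the ICU-stay model.
2. State which model part carries the tested treatment effect.
3. Replace the plain Poisson count part with one that estimates dispersion. Either use Poisson among ventilated patients with Pearson-scaled standard errors and a t reference, alongside a separate comparison of the proportion ventilated; or use a zero-inflated negative binomial.
4. Say whether this variable belongs to the Hochberg family.

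The scaled Poisson is the simpler choice. Under no effect it rejected in 4.0% to 5.4% of data sets in all 30 settings tried (five duration shapes, two units, and 75%, 50% or 30% ventilated), with no dispersion cut-off or data-dependent fallback. A negative binomial count part also largely removes the dependence on the unit, with a Wald-test size of 6.0% to 6.2% in days and 6.7% to 7.0% in hours for the gamma shape. Like the count part of the present model, the scaled Poisson compares ventilated patients only, so it should be reported with the proportion ventilated.

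The cost is a few SAP sentences and no new data. Intervals widen somewhat: at 75% ventilated, the 95% factor for the ratio in days goes from about 1.20 to about 1.24.

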### Secondary Endpoints (objectives)

The secondary objectives of this study are as follows:

- To evaluate the effects of intravenous L-Citrulline on plasma levels of citrulline and arginine in patients admitted to the hospital with COVID-19 infection (SARS-CoV2) and acute hypoxemic respiratory symptoms requiring oxygen therapy.
- To evaluate beneficial effect of intravenous L-Citrulline on hemodynamics.
- To evaluate the safety of intravenous L-Citrulline compared to placebo as measured by incidence of reported adverse events.
- To evaluate the effect of intravenous L-Citrulline compared to placebo as measured by the total length of all mechanical ventilation, including non-invasive modalities such as high flow nasal cannula and BiPAP and oxygen therapy.

- To evaluate the effect of intravenous L-Citrulline compared to placebo on Hospital all-cause mortality
- To evaluate the effect of intravenous L-Citrulline compared to placebo on lengths of ICU and hospital stay
- To evaluate overall difference in intubation rates
- To evaluate overall duration of mechanical ventilation from consent and post-infusion

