## **SAMPLE SIZE**

This study will accrue approximately 66 patients in a 1:1 fashion to account for 10% attrition. This sample size was determined on the basis of an expected time to intubation event in the placebo group derived from historical data on critically ill patients with COVID-19 infection (SARS-CoV-2) of 3 days (72 hours) +/- 3 days (72 hours). An acceptable effect size in the intravenous citrulline group would be delay in time to an intubation event of at least 6.5 days (156 hours). Thus, a two-sided log-rank test with an overall sample size of 60 patients achieves 81% power at a 0.05 significance level to detect a hazard ratio of 0.46 when the placebo group time to intubation is 3 days. The study is expected to last 12 months, of which patient accrual will occur in the first 6-9 months. The accrual pattern across time is uniform.

In terms of mortality, in patients who progress to acute hypoxic respiratory failure requiring ICU care, the mortality is 50%. With a sample size of 60 patients, the study will have 80% power to detect a difference between the group proportions of -33%. The mortality in the intravenous citrulline group is assumed to be 50% under the null hypothesis and 17% under the alternative hypothesis. Again, the mortality rate for the placebo group is assumed to be 50%. The test statistic used is the two-sided z-test with pooled variance with a 0.05 significance level.

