## **ANALYSIS CONVENTIONS**

### **Statistical Significance**

Unless otherwise specified, statistical tests will be 2-sided for all analyses and the null hypothesis will be rejected at the significance level of  $\alpha = 0.05$ . P-values will be rounded to four decimal places before assessing statistical significance. In this Phase II study, no adjustment for multiple comparisons for the primary clinical, safety, and biochemical outcomes will be made. The multiplicity from testing secondary clinical, biochemical, and safety outcomes will be adjusted based on a Hochberg procedure (Sakamaki, 2013; Ye et al., 2012).

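### The zero-inflated Poisson model for overall duration of mechanical ventilation has no named treatment test, and none of its parameters or its joint test corresponds to overall mean duration

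*SAP*

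**What the plan says.** One SAP objective is "To evaluate overall duration of mechanical ventilation from consent and post-infusion". The analysis is given under Length of Non-invasive Mechanical Ventilation. The reason for the model is that "There is an expectation that some patients will not require mechanical ventilation", so patients never ventilated stay in as zeros, and "overall duration of mechanical ventilation will be modeled with a zero-inflated Poisson model using consent and post-infusion start time for two separate analysis". Protocol 10.6.1 is slightly wider: "Overall duration of mechanical ventilation will be modeled with zero-inflated Poisson or negative binomial method".

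Neither document says whether treatment enters the zero part, the count part or both. Neither says which coefficient or test gives the p-value, what effect is reported, or in what unit. By contrast, the SAP section on Length of ICU Stay names the quantity compared (expected stay) and the estimate reported (a group mean difference with 95% CI).

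The SAP section on Statistical Significance applies a Hochberg procedure to the secondary outcomes. Prevention of ventilation is tested separately: by the stratified log-rank test and Cox model for the primary endpoint, and by Fisher's exact tests on the proportions intubated or ventilated.

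**The concern.** The natural reading of overall duration in an intention-to-treat trial is ventilation time over everyone randomised, with zero for a patient who never needed it. A ZIP model splits that quantity in two and has no treatment coefficient for the whole.

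The count part is the only part that carries duration. Its treatment coefficient compares patients who were ventilated, a group selected after randomisation by the event that the drug is meant to prevent. If the drug prevented mainly the milder cases, those still ventilated would run longer and the coefficient would point to harm, even with total ventilation time unchanged or lower. A negative binomial count part would not change this.

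Hochberg needs one p-value per outcome. Here several candidates exist and none is named. Protocol 10.5 also mentions overall duration of mechanical ventilation as an alternative primary clinical endpoint, which raises the stakes, although the SAP makes time to intubation the sole primary endpoint.

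**Working it through.** **Inputs.** The SAP sample size section gives the patient number: "a two-sided log-rank test with an overall sample size of 60 patients", hence 30 per arm. "Unless otherwise specified, statistical tests will be 2-sided for all analyses", at 0.05. The case series in protocol 3.4 (24 critically ill adults) gives 18/24 = 75% ventilated and a median of 10 days, IQR 7–12. I assume a mean of 10 days and SD (12 − 7)/1.35 = 3.7 days.

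**The plan's own figure.** The sample size "achieves 81% power at a 0.05 significance level to detect a hazard ratio of 0.46". By Freedman's formula with all 60 patients having an event: √60 × (1 − 0.46)/(1 + 0.46) − 1.96 = 7.746 × 0.3699 − 1.96 = 0.905, and Φ(0.905) = 81.7%. This reproduces the stated figure. It concerns time to intubation; the plan gives no power for ventilation duration.

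**What ZIP parameters measure.** Let π be the structural-zero probability and λ the count mean.

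- P(Y = 0) = π + (1 − π)e^(−λ), and E(Y) = (1 − π)λ.
- At λ = 10, e^(−10) ≈ 0.00005, so practically every zero is a never-ventilated patient and λ is mean duration among the ventilated.
- Count coefficient: log(λ₁/λ₀). Zero coefficient: the difference in logit π.
- Log ratio of overall means: log[(1 − π₁)/(1 − π₀)] + log(λ₁/λ₀).

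Equality of overall means requires (1 − π₁)λ₁ = (1 − π₀)λ₀. The count null (λ₁ = λ₀) and the zero null (π₁ = π₀) are different conditions. The joint null (both at once) implies equal overall means, but equal overall means do not imply the joint null.

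**Pure prevention.** With 75% against 40% ventilated and 10 days each, overall means are 7.5 and 4.0 days, yet the count coefficient is exactly zero.

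**Equal overall duration.** 75% × 10 = 7.5 days and 56.25% × 13.33 = 7.5 days, yet both coefficients are non-zero.

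**Simulation.** 30 per arm, 3,000 to 4,000 trials per scenario, durations in days, treatment in both ZIP parts. The comparator is a Welch test of means with zeros included. Ranges cover Poisson and gamma durations and repeated runs. Monte Carlo error is up to about 2 points.

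| Scenario (placebo vs citrulline) | Overall means, days | Count coefficient rejects | Joint 2-df test rejects | Welch rejects |
|---|---|---|---|---|
| 75% vs 45%, 10 d each | 7.5 vs 4.5 | 5–10% | 58–61% | 54–59% |
| 75% vs 40%, 10 d each | 7.5 vs 4.0 | 5–10% | 71–74% | 68–72% |
| 75% vs 35%, 10 d each | 7.5 vs 3.5 | 5–10% | 83–84% | 80–82% |
| 75% × 10 d vs 56% × 13.3 d | 7.5 both | 84–87% | 86–89% | about 5% |
| 60% × 8 d vs 40% × 12 d | 4.8 both | 92% | 93% | 5.5% |
| 50% × 8 d vs 40% × 10 d | 4.0 both | 41% | 38% | 5.3% |

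In the first three rows the zero part rejects in about 67%, 80% and 90%. The upper end of the count column there is not power: with gamma durations (SD 3.7) the count test also rejects in 9–10% when the arms are identical. In the fourth row some runs, under other assumptions about spread, gave 78–79% for the count coefficient and 83% for the joint test. Repeating that row from a 30% placebo rate gives about 40–49% for both.

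**The case against.** A reader might infer that the SAP tests duration only among ventilated patients, cannot see prevention, and so loses 46 to 76 points of power. The documents do not support that. They name a model, not a tested coefficient. With treatment in the zero part, that part detects prevention, and the joint test has about the same power as a comparison of means. The large loss applies only if the count coefficient alone is the test.

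Other points that stand:

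- Prevention is the primary endpoint and has its own Fisher tests, so a null duration coefficient would not hide that benefit.
- The objective does not spell out a mean over all patients with zeros. Overall could also mean all modalities: another objective covers "the total length of all mechanical ventilation, including non-invasive modalities such as high flow nasal cannula and BiPAP and oxygen therapy". If non-invasive support counts, there will be fewer zeros, and figures for invasive ventilation describe the variable less well.
- The series was critically ill and its 75% includes three patients with do-not-intubate directives. The trial enrols patients on the floor without intubation.
- The equal-means case is constructed. A rejection there finds a real difference in duration among the ventilated: it answers a different question and is not a false positive about that group.
- A ZIP model with treatment in both parts can yield the ratio of overall means as a derived estimate. The plan does not ask for it.

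What the objection does not rescue is the link from model to objective. The zero part ignores duration and repeats the Fisher comparison. The joint test gives no single direction or estimate and rejects often when overall duration is equal. Testing prevention elsewhere does not answer how long patients were ventilated overall.

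**Conclusion.** The point holds as a mis-targeted and under-specified secondary analysis. It should be corrected, but it does not touch the primary result. Whichever standard ZIP test is chosen, it does not test equality of overall mean duration.

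The algebra needs only that durations among the ventilated are long enough for Poisson zeros to be negligible. The rejection rates rest on assumed ventilation rates and durations: when overall means are equal, mis-targeted rejection ranges from about 38% to above 90% across the scenarios tried. The claim of no power for prevention is conditional on the count coefficient being the test, which the SAP leaves open.

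The point is separate from over-dispersion, which is a further weakness of Poisson standard errors. With identical arms and SD 3.7 days, the count test rejects in 9–10% if duration is in days and 73–75% if in hours, and the SAP states no unit for overall duration.

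**What to change.** In the SAP section on Length of Non-invasive Mechanical Ventilation and in protocol 10.6.1, before database lock:

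- Define the comparison as mean overall duration across all randomised patients, zeros included. State the unit and whether non-invasive support counts.
- Name one method: a log-link GLM with robust standard errors, a marginalised zero-inflated model, or a Welch or bootstrap contrast of means.
- Report the ratio or difference of overall means with 95% CI, and name the single p-value that enters Hochberg, including which of the two time origins supplies it.
- Show duration among ventilated patients descriptively, without a test.
- State how death is handled, since an early death shortens ventilation time. Comparing means does not resolve this by itself.

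A van Elteren rank test should not be offered as equivalent, because it does not test equality of means.

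The cost is a few lines of text and a different model call on the same data. The headline estimate will no longer isolate duration given ventilation. The choice of method also affects power: in the prevention scenarios the robust log-link GLM reached 45–77% against 52–83% for Welch, about 5 to 8 points less, so the Welch power figures should not be carried over to it.
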